4.3 Restrictions

There will be no special restrictions for subjects participating in this study. Subjects are to maintain their normal or recommended renal diets per standard of care, medications (with the exception of those listed in Section 5.4), and activities of daily living as determined by the investigator.

4.4 Reproductive Potential

4.4.1 Female Contraception

Sexually active females of child-bearing potential should be using an acceptable form of contraception, as described below. Females of child-bearing potential must be advised to use acceptable contraceptives from the time of screening and through 3 months following the last dose of investigational product. If hormonal contraceptives are used they should be administered according to the package insert. Females of child-bearing potential who are not currently sexually active must agree to use acceptable contraception, as defined below, if they become sexually active during the period of the study from the time of screening and for 3 months following the last dose of investigational product.

Female subjects should be either:

- Post-menopausal (12 consecutive months of spontaneous amenorrhea)
- Surgically sterile (having undergone one of the following surgical acts: hysterectomy, bilateral tubal ligation, bilateral oophorectomy, or bilateral salpingectomy) and at least 6 weeks post-sterilization, or
- Females of child-bearing potential with a negative urine pregnancy test (confirmed by a negative serum beta-HCG pregnancy test) at the Screening Visit and a negative urine pregnancy test at the Day 1 Visit. Females of child-bearing potential must agree to abstain from sexual activity that could result in pregnancy or agree to use acceptable methods of contraception.

Acceptable methods of contraception are:

- Intrauterine devices plus condoms

- Double-barrier methods (eg, condoms and diaphragms with spermicidal gel or foam)
- Hormonal contraceptives (oral, depot, patch, injectable, or vaginal ring), stabilized for at least 30 days prior to the Screening Visit, plus condoms. Note: if subject becomes sexually active during the study, they should use one of the other acceptable methods noted above in addition to the hormonal contraceptive until it has been stabilized for 30 days.

4.4.2 Male Contraception

Male subjects will be required to use a condom in conjunction with spermicidal gel, foam, cream, film, or suppository from time of dosing until 3 months after the last dose of investigational product. Child-bearing female partners of male study participants will be required to follow the acceptable methods of contraception for this study (described in Section 4.4.1) from the time of first dosing until 3 months after the last dose of investigational product. For male subjects, sexual intercourse with pregnant partners should also be avoided during the course of the study unless condoms are used from the time of the first dose until 3 months after the last dose of investigational product. Male subjects must not donate sperm until 3 months after the last dose of investigational product.

4.5 Discontinuation or Withdrawal of Subjects

A subject may withdraw from the study at any time for any reason without prejudice to their future medical care by the physician or at the institution. The investigator or sponsor may withdraw the subject at any time (eg, in the interest of subject safety). The investigator is encouraged to discuss withdrawal of a subject from the study with the medical monitor when possible.

If a subject is discontinued from the study (not only from treatment) for any reason prior to the Month 6 follow-up Visit, every effort will be made to obtain AEs, serum BUN and Cr results, eGFR_{MDRD}, and a biopsy to send to the pathology and nephrology EACs for determination of TG and graft function status, respectively (see Table 2 for Early Discontinuation Visit procedures). If a subject is discontinued from treatment for any reason for the remainder of a treatment cycle for before receiving 7 doses, the subject will continue in the study and no Early Discontinuation Visit will be performed. In this instance, the next scheduled treatment visit in the treatment cycle should be conducted and all procedures for that visit should be performed other than those related to study drug administration, and the scheduled Day 25 post-treatment visit will follow (any remaining treatment visits for that cycle are not required). If a subject is discontinued from the study for any reason after the Month 6 visit and prior to the end of the study at 4 years, every effort will be made to obtain AEs, serum BUN and Cr and eGFR_{MDRD} results to send to the nephrology EAC for determination of graft function status (see Table 2 for End of Study Visit procedures).

Whenever possible and with the consent of the subject, the investigator will attempt to obtain information on graft and subject survival status from discontinued subjects at remaining scheduled assessment times through Month 48. The reason for termination, date of stopping investigational product, and the total amount of investigational product taken must be recorded in the case report form (CRF) and source documents.

Subjects who discontinue will not be replaced. Approximately 112 eligible subjects with biopsy-proven AMR will be randomized to provide 56 subjects per treatment arm. Additional eligible subjects may be enrolled based on the interim data analysis of the first 30 subjects who complete the Month 6 TG assessment (Section 9.5.1).

4.5.1 Reasons for Discontinuation and/or Withdrawal

The reason for investigational product early discontinuation and/or withdrawal from the study must be determined by the investigator and recorded in the subject's medical record and in the CRF. In the case of early discontinuation of the medicinal product and/or withdrawal from the study for more than 1 reason, each reason should be documented in the source document and the most clinically relevant reason should be entered in the CRF.

Reasons for discontinuation include but are not limited to:

- Adverse event
- Protocol violation
- Consent withdrawal by subject
- Other, specify (e.g., pregnancy, etc.)

4.5.2 Subjects 'Lost to Follow-up' Prior to Last Scheduled Visit

A minimum of 3 documented attempts must be made to contact any subject lost to follow-up at any timepoint prior to the last scheduled study visit (office visit or telephone contact). At least 1 of these documented attempts must include a written communication sent to the subject's last known address via courier or mail (with an acknowledgement of receipt request) asking that they return to the site for final safety evaluations.

4.5.3 Stopping Rules

If any of the clinically significant thrombotic or thromboembolic events listed below (exclusive of superficial thrombophlebitis, dialysis access clotting, or catheter-related thrombotic events) is reported as a study-drug-related SAE in any subject, as defined by the Principal Investigator at the site and confirmed through a diagnostic examination as indicated in section 8.2.4, enrollment of new subjects will be halted.

- Renal allograft arterial or venous thrombosis
- Deep vein thrombosis
- Myocardial infarction
- Pulmonary embolism
- Ischemic cerebrovascular accident (stroke), or transient ischemic attack (TIA), exclusive of cerebrovascular hemorrhage (subarachnoid or subdural hemorrhage)
- Any large vessel thrombosis (exclusive of the presence of an indwelling catheter)

Study procedures for subjects already randomized will continue, including treatment according to their assigned dosing regimen.

The DMC will perform a safety review of this specific event and of the patient population included in the study and will forward its recommendation to the Sponsor about the opportunity, in terms of patient safety, of restarting enrollment. Enrollment may be restarted by the Sponsor in consultation with the DMC.

Please see Section [8.2.4](#) and [Appendix 4](#) for further information on thrombotic and thromboembolic events.

5. CONCOMITANT AND POST-TREATMENT MEDICATIONS

5.1 Concomitant Medications

All prescription and over-the-counter medications will be recorded in the CRF as concomitant medications from 2 weeks prior to the first dose of investigational product (Day 1) through the day of the last dose of investigational product (Day 13) for each treatment period (Table 1). Medications used to treat AEs or SAEs, regardless of relatedness of the AEs/SAEs to investigational product, will be recorded through 30 days after the last dose of investigational product for each treatment period. AEs of special interest and the medications listed in Section 5.3 and 5.5 will be recorded for the duration of the study. Topical medications will be recorded only if used for treatment of an AE. Prophylactic treatment for deep vein thrombosis (DVT) (including mechanical treatment, eg, compression) will also be collected through the duration of the study.

Administration of the following will not be recorded unless the investigator considers this important to the assessment of an AE:

- Intravenous fluids
- Enteral or parenteral nutrition
- Vitamins or other dietary supplements
- Electrolyte supplementation
- Oxygen

5.2 Concomitant Blood Products

The dates and amount of the following blood products will be recorded in the CRF if administered from the day of the first dose of investigational product (Day 1) through the day of the last dose of investigational product (Day 13) for each treatment period (Table 1):

- Albumin
- Packed red blood cells
- Whole blood
- Fresh frozen plasma
- Cryoprecipitate
- Platelets

5.3 Immunosuppressive Agents or Treatments

From the day of the first dose of investigational product (Day 1) through Year 4, the following concomitant medications will be collected in the CRF:

- Any IV or oral steroids

- Rituximab
- Bortezomib
- Muromonab-CD3
- Alemtuzumab
- Anti-thymocyte globulin (rabbit)
- Lymphocyte immune globulin, anti-thymocyte globulin (equine)
- Any sucrose-free IVIg preparation
- Plasmapheresis, plasma exchange, or immune adsorption treatments
- Daclizumab or basiliximab
- Tacrolimus and Cyclosporine
- Mycophenolate mofetil and mycophenolic acid
- Azathioprine
- Other immunosuppressive agents (specify)

5.4 Prohibited Medications

Use of the following agents is prohibited from Day 1 through the EOS evaluation:

- Sucrose-containing IVIg
- Any C1 INH: plasma-derived (eg, Berinert[®], Ceter[®]) or recombinant (eg, Rhucin[®])
- Eculizumab (Soliris[®])
- Ecallantide (Kalbitor[®])
- Any unapproved/investigational biologic agent or drug

5.5 Other Medications

From the day of the first dose of investigational product (Day 1) through Year 4, the following concomitant medications will be collected in the CRF:

- Ace-inhibitors (eg, Capoten, Vasoten, Lotensin), sartans (eg, Diovan, Micardis), renin inhibitors (eg, Tekturna)
- Antiplatelet medications (eg, ASA, Plavix, Ticlid)
- Anticoagulant agent (eg, Comadin, Xarelto)

6. INVESTIGATIONAL PRODUCT

6.1 Identity of Investigational Product

The test product is CINRYZE, which will be provided by the sponsor as a lyophilized powder of 500 U C1 INH/vial. Vials of CINRYZE also contain the following inactive ingredients: trisodium citrate, sodium chloride, L-Valine, L Alanine, L-Threonine, and sucrose. Each vial of CINRYZE will be reconstituted with sterile water for IV injection and administered with 0.9% sodium chloride solution for infusion.

The placebo product is 0.9% sodium chloride solution for infusion.

Additional information is provided in the pharmacy manual.

6.1.1 Blinding the Treatment Assignment

Qualified subjects will be randomized in a 1:1 ratio to receive CINRYZE or placebo using a centralized procedure. An Interactive Voice/Web Response System (IV/WRS, IRT) will be used to randomize subjects and provide the treatment assignment to the unblinded pharmacist. The unblinded pharmacist will prepare the blinded IV solution (CINRYZE or placebo) accordingly.

A Sponsor representative(s) not affiliated with the core team will be unblinded to treatment assignment in order to review drug accountability on an ongoing basis throughout the study (Section 6.4). This unblinded representative will remain independent of other study activities.

For the first interim analysis, the EACs, sponsor, investigator, and subjects will be blinded to the study treatment. When the criterion to conduct the second interim analysis is met, treatment assignment for those subjects will be unblinded to designated sponsor representatives for analysis. The treatment assignments for all other subjects will be blinded to the EACs, investigator, and subjects during the conduct of the study.

6.1.2 Commercially Obtained Investigational Product

CINRYZE product approved for commercial distribution in the US and sterile water for injection will be labeled for clinical use and supplied by the sponsor.

Mix 2 transfer devices for reconstitution will also be supplied by the sponsor.

Sites will be responsible for sourcing 0.9% sodium chloride solution for infusion of either the active drug or the placebo.

6.2 Administration of Investigational Product(s)

Reconstitution and administration instructions for CINRYZE will be provided as a separate document to investigative sites.

6.2.1 Interactive Voice/Web Response System Technology for Investigational Product Management

An IV/WRS (IRT) will be employed in this study to manage the tracking and confirmation of shipment, supply, inventory, ordering, expiration, and site-assignments of the investigational product. The IV/WRS provider will provide a user manual and training to each site, with detailed instruction on the use of the IV/WRS.

6.2.2 Allocation of Subjects to Treatment

This is a double-blind, placebo-controlled study. The actual treatment given to individual subjects is determined by a randomization schedule automatically assigned by the IV/WRS (IRT).

Subject numbers are assigned to all subjects as they consent to take part in the study. Within each level of the severity of AMR and donor characteristic (as defined in the paragraph below) across sites, the subject number is assigned to subjects according to the sequence of presentation for study participation. Subject number is unique within a protocol.

The randomization number represents a unique number corresponding to investigational product allocated to the subject, once eligibility has been determined. A randomization number will be assigned by the IV/WRS at the Baseline Visit (Day 1) after subject eligibility has been confirmed using the randomization criteria. The randomization schedule will be stratified for (1) living vs deceased donor and (2) severity of acute AMR as defined by the screening period $eGFR_{MDRD} \leq 15 \text{ mL/min/1.73m}^2$ (severe) or $>15 \text{ mL/min/1.73m}^2$ (mild to moderate).

6.2.3 Dosing

Eligible subjects in this study will receive a total of 7 doses of investigational product over a 13-day period: an initial 100 mL IV infusion containing 5000 U CINRYZE or placebo (100 mL 0.9% sodium chloride for infusion) on Day 1, followed by 2500 U of CINRYZE in 100 mL of IV infusion or placebo (100 mL 0.9% sodium chloride for infusion) IV on Days 3, 5, 7, 9, 11, and 13 (Table 4). If DSA reduction therapy occurs on the same day as investigational product dosing, investigational product will be administered after completion of the plasmapheresis, plasma exchange or immune adsorption treatment session and dosing of the sucrose-free IVIg.

Table 4 Investigational Product Dosing Day, Volume and Amount

	Volume	CINRYZE	Placebo
Day 1	100 mL	5000 Units of CINRYZE (50 mL of CINRYZE/ 50 mL of normal saline)	100 mL of normal saline
Day 3, 5, 7, 9, 11, and 13	100 mL	2500 Units of CINRYZE (25 mL of CINRYZE/ 75 mL of normal saline)	100 mL of normal saline

Note: All doses must be brought up to 100 mL

Additionally, if a study subject has resolution of their qualifying episode of acute AMR and, during the first 180 days after the biopsy of the qualifying episode of AMR, has a new episode of AMR as defined in Section 3.1, the subject may be retreated with investigational product per the same randomization assignment per protocol.

6.2.4 Unblinding the Treatment Assignment

The treatment assignment must not be broken during the study except in the following situations:

1. Emergency situations where the identification of the investigational product is required for further treatment of the subject. The investigator should contact the Sponsor's representative(s) not affiliated with the core team as soon as possible after the subject has been unblinded.
2. The first interim analyses for sample size re-estimation after the first 30 subjects complete the Month 6 TG assessment. Only the DMC members will be unblinded for this interim analysis.
3. The second interim analysis is conducted when an adequate number of subjects complete the Month 6 TG assessment for the primary endpoint. The adequate number of subjects will be determined based on the first interim analysis. When the criterion to conduct the second interim analysis is met, treatment assignment for those subjects will be unblinded to designated sponsor representatives for analysis. The treatment assignments for all other subjects will be blinded to the EACs, investigator, and subjects during the conduct of the study.
4. When approximately 50% (~26 events), 75% (~39 events), and 100% (~51 events) of the study information (ie, total number of subjects with all-cause graft failure) is collected. Only the DMC members will be unblinded for the 50% and 75% time points in these interim analyses.

In the event that the treatment assignment is broken, the date, the signature of the person who broke the code, and the reason for breaking the code are recorded on the source documents. Upon breaking the blind, the subject is withdrawn from the study, but should be followed up for safety purposes. Any code-breaks that occur must be reported to the contract research organization (CRO) and the Sponsor's representative(s). Code-break information is held by the pharmacist/designated person at the site and by the CRO Medical Monitor for the study or designee.

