3.2 Duration and Study Completion Definition

The duration of the study will be event driven, and is based upon an assumption that there will be approximately 51 all-cause graft failures that will be adjudicated by the nephrology EAC. The trial will continue until 51 such events are accrued and adjudicated by the nephrology EAC. See Section 9.5.2 for additional details. However the maximum amount of time each subject will be followed in the study will be 4 years post initial treatment with investigational product. Subjects will complete visits every 6 months until the study is ended.

If a subject is discontinued from the study (not only from treatment) for any reason prior to the Month 6 follow-up Visit, every effort will be made to obtain AEs, serum BUN and Creatinine results, eGFR_{MDRD}, and a biopsy to send to the pathology and nephrology EACs for determination of TG and graft function status, respectively (see [Table 2](#) for Early Discontinuation Visit procedures). If a subject is discontinued from treatment for any reason for the remainder of a treatment cycle before receiving 7 doses, the subject will continue in the study and no Early Discontinuation Visit will be performed. In this instance, the next scheduled treatment visit in the treatment cycle should be conducted and all procedures for that visit should be performed other than those related to study drug administration, and the scheduled Day 25 post-treatment visit will follow (any remaining treatment visits for that cycle are not required). If a subject is discontinued from the study for any reason after the Month 6 visit and prior to the end of the study at 4 years, every effort will be made to obtain AEs, serum BUN and Cr and eGFR_{MDRD} results to send to the nephrology EAC for determination of graft function status (see [Table 2](#) for End of Study Visit procedures).

The subject's maximum duration of participation is expected to be approximately 4 years.

The Study Completion Date is defined as the date the final subject, across all sites, completes their final protocol-defined assessment. Please note that this includes the follow-up visit or contact, whichever is later. The Study Completion Date is used to ascertain timing for study results posting and reporting.

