8.1.7 Pregnancy

All pregnancies are to be reported from the time informed consent is signed and throughout the defined post-treatment follow-up period stated in Section 7.1.3.

Any report of pregnancy for any female study participant or the partner of a male study participant must be reported within 24 hours to the Shire Pharmacovigilance Department using the Shire Investigational and Marketed Products Pregnancy Report Form. A copy of the Shire Investigational and Marketed Products Pregnancy Report Form (and any applicable follow-up reports) must also be sent to the CRO/Shire Medical Monitor using the details specified in the [emergency contact information](#) section of the protocol. The pregnant female study participant must be withdrawn from the study.

Every effort should be made to gather information regarding the pregnancy outcome and condition of the infant. It is the responsibility of the investigator to obtain this information within 30 calendar days after the initial notification and approximately 30 calendar days post-partum.

Pregnancy complications such as spontaneous abortion/miscarriage or congenital abnormality are considered SAEs and must be reported using the Shire Clinical Trial Serious Adverse Event Form. NOTE: An elective abortion is not considered an SAE.

In addition to the above, if the investigator determines that the pregnancy meets serious criteria, it must be reported as an SAE using the Shire Clinical Trial Serious Adverse Event Form as well as the Shire Investigational and Marketed Products Pregnancy Report Form. The test date of the first positive serum/urine beta-HCG test or ultrasound result will determine the pregnancy onset date.

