9.8.2 Secondary Efficacy Endpoints

9.8.2.1 Key Secondary Efficacy Endpoint

The key secondary endpoint is defined as the proportion of subjects with all-cause graft failure (ie, return to permanent dialysis and/or removal of the transplanted kidney and/or clinical determination of cessation of graft function) at 4 years following treatment of the initial qualifying AMR episode. The FAS population will be used to report the efficacy data for all-cause graft failure. Subjects who do not have the key secondary efficacy endpoint assessed post-dose will be assigned as failures.

The proportion of subjects with all-cause graft failure will be summarized by treatment group. Subjects with an assessment of all-cause graft failure or who drop out due to graft failure will be included in the hypothesis testing.

The test statistics and boundary values for decision making at the 3 analyses (2 interim and 1 final) will be specified in the SAP.

The null hypothesis for the proportion of subjects with all-cause graft failure post-treatment will be tested at the overall accumulative alpha level of 0.025 (1-sided test). This hypothesis will only be tested if testing for the primary endpoint of new or worsening TG at 6 months of initiation of treatment is statistically significant.

A number of sensitivity analyses will be performed to assess any impact on the key secondary endpoint results, inference, and conclusions due to missing data. In addition, descriptive analyses on the key secondary endpoint will be provided in selected subgroups.

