## 10.2 Key Secondary Efficacy Endpoint(s) and Analysis

The key secondary endpoint is defined as the proportion of subjects with all-cause graft failure at 4 years following treatment of the initial qualifying AMR episode. The graft failure is defined as 1 or more of the following: (1) institution of permanent dialysis, (2) current transplant nephrectomy, or (3) clinical determination of cessation of kidney graft function in any subject that had received a pre-emptive kidney transplant prior to starting dialysis. The FAS will be used for analyzing the key secondary endpoint. Subjects who discontinued prior to 4 years (i.e. Month 48) will be considered 'missing assessment for graft failure at 4 years' and assigned as failures.

The hypothesis of the key secondary endpoint will only be tested if the testing for the primary endpoint of new or worsening TG at 6 months is statistically significant.

The key secondary analysis specified below will be performed based on the FAS. As a sensitivity analysis, the key secondary analysis will be also performed based on Per-protocol Analysis Set-2.

The key secondary endpoint will be presented as the proportion of subjects with all-cause graft failure, and their difference between treatments ( $\Delta_{Cinryze-Placebo}$ ) is defined as follows:

$$\Delta_{Cinryze-Placebo} = \Pi_{Cinryze} - \Pi_{Placebo}$$

Where  $\Pi_{Cinryze}$  is the proportion of all-cause graft failure post-treatment in the CINRYZE group and  $\Pi_{Placebo}$  is the proportion of all-cause graft failure post-treatment in the placebo group.

The analysis will employ a type I error rate of 0.025 to test null hypothesis:

$$H_0 : \Pi_{Cinryze} - \Pi_{Placebo} \geq 0$$

Against the 1-sided alternative:

$$H_a : \Pi_{Cinryze} - \Pi_{Placebo} < 0$$

The key secondary endpoint will have 3 analyses (2 interim and 1 final), at approximately 50% (~26 events), 75% (~39 events) and 100% (~51 events) of the targeted all-cause graft failure. The purpose of the interim analyses is to consider early stopping of the study for claiming of efficacy.

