The difference between treatments will be evaluated by a Fisher's Exact test. If the p-value from the test is  $\leq 0.0030$  at first interim analysis (~50% of events), or  $\leq 0.0075$  at the second interim analysis (~75% of events), or  $\leq 0.0221$  at the final analysis (~100% of events), it will be concluded that CINRYZE is efficacious based on the proportion of subjects with all-cause graft failure and the result will serve as confirmatory evidence of clinical benefit based on all enrolled subjects.

Sensitivity analyses will be done at final analysis by using multiple imputation (MI) assuming missing at random (MAR) to assign missing key secondary endpoint and/or by using Cochran–Mantel–Haenszel (CMH) test for treatment effect. The CMH model will assess the treatment effect with controlling for (1) donor characteristic (living vs deceased), (2) baseline AMR severity (severe vs mild to moderate), and possibility (3) time to onset of qualifying AMR from current transplant ( $>100$  days vs  $\leq 100$  days) if degree of freedom allows. All the sensitivity analyses defined below will be based on the FAS.

	Statistical Test	Logic to assign the missing assessments for graft failure at 4 years (i.e. discontinued prior to 4 years)
Key Secondary Analysis Model	Fisher's Exact	Assign failure for subjects who discontinued prior to 4 years.
Sensitivity analysis 1	Fisher's Exact	MI for subjects who discontinued prior to 4 years.
Sensitivity analysis 2	CMH	Assign failure for subjects who discontinued prior to 4 years.
Sensitivity analysis 3	CMH	MI for subjects who discontinued prior to 4 years.

For multiple imputation for the key secondary endpoint, a monotone missing pattern will be assumed. The prediction model will consider treatment group, , AMR severity baseline, donor characteristic as factors with available post-dose eGFR results incorporated. The imputation seed will be 83789524 and number of imputations will be set as 100.

For sensitivity analysis 1, multiple imputation will be used to impute the key secondary endpoint outcome for all subjects who discontinued prior to 4 years. The p-values from Fisher's Exact tests will be computed for each imputed dataset and transformed to  $\chi^2$ -distribution with  $df = 2$  using Fisher's transformation as:

$$\Psi^{(m)} = -2 \log(p^{(m)}) \sim \chi_2^2$$

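### Subjects withdrawn from the study for a code break or pregnancy are counted as graft failures at 4 years, even when the graft is known to be working

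*Protocol*

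**What the plan says.** **Who leaves the study.** On code breaks, Protocol 6.2.4 states: "Upon breaking the blind, the subject is withdrawn from the study, but should be followed up for safety purposes". On pregnancy, Protocol 8.1.7 states: "The pregnant female study participant must be withdrawn from the study". For a subject who stops dosing for other reasons, Protocol 3.2 does the opposite: "the subject will continue in the study and no Early Discontinuation Visit will be performed". Protocol 4.5 repeats the rule in 3.2.

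**What is still collected.** For subjects who discontinue, Protocol 4.5 says that, where possible and with consent, "the investigator will attempt to obtain information on graft and subject survival status from discontinued subjects at remaining scheduled assessment times through Month 48".

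**How they are scored at 4 years.** Protocol 9.8.2.1 says: "Subjects who do not have the key secondary efficacy endpoint assessed post-dose will be assigned as failures". SAP 10.2 is wider. Its rule begins "Subjects who discontinued prior to 4 years (i.e. Month 48) will be considered" and goes on to class these subjects as missing and count them as failures. Its table gives the main model as "Assign failure for subjects who discontinued prior to 4 years" and sensitivity analyses 1 and 3 as "MI for subjects who discontinued prior to 4 years".

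**How they are scored at Month 6.** SAP 10.1 counts a subject with no 6-month transplant glomerulopathy (TG) assessment as having new or worsening TG.

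**The concern.** Dosing lasts 13 days per episode and follow-up runs to 4 years. For nearly all of that time there is no dosing to stop, so withdrawal from the study mainly ends outcome follow-up. Protocol 8.1.7 has pregnancies reported throughout post-treatment follow-up, so the rule can apply long after the last dose.

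Taken together, the texts turn an administrative exit into an endpoint event. A subject is unblinded or becomes pregnant, leaves the study with a working graft, and is entered as a graft failure. SAP 10.2 makes no exception where the site has obtained graft status under Protocol 4.5. The two documents can therefore give the same subject different values: not a failure under Protocol 9.8.2.1, a failure under SAP 10.2. At stake are the accuracy of the key secondary endpoint and some of its power.

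**Working it through.** **Inputs.** All-cause graft failure 68% on placebo and 34% on CINRYZE; 90% power at 1-sided 0.025 with 100 subjects; 10% dropout; 112 randomized, 56 per arm; 51 events (Protocol 9.6, SAP 2.5). Fisher's exact test at a final 1-sided level of 0.0221 (SAP 2.6 and 10.2).

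**Reproducing the plan.**
- Rates: 1 - (1 - 0.64)(1 - 0.12) = 0.683 and 1 - (1 - 0.25)(1 - 0.12) = 0.340.
- Sample size: the two-proportion formula with continuity correction gives 50 per arm, so 100.
- Dropout: 100/0.90 = 111.1, taken to 112.
- Events: 50 × 0.68 + 50 × 0.34 = 34 + 17 = 51.

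All the stated figures reproduce. Exact Fisher power at 50 per arm is 91.5% at 0.025 and 89.4% at 0.0221.

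**Effect of one withdrawn subject.** If withdrawal is unrelated to graft outcome, a withdrawn subject would have kept the graft with probability 1 - p. The expected number of false failures per withdrawn subject is 1 - 0.34 = 0.66 on CINRYZE and 1 - 0.68 = 0.32 on placebo. A single false failure moves an arm's rate by 1/56 = 1.8 points.

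**Effect of a share d.** If a share d of an arm is withdrawn and scored as failed, the rate becomes p' = p + d(1 - p). At d = 5%:
- placebo 0.68 + 0.05 × 0.32 = 0.696
- CINRYZE 0.34 + 0.05 × 0.66 = 0.373
- difference 0.323

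Exact Fisher power at 56 per arm and 1-sided 0.0221, ignoring the interim looks:

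| Assumed share withdrawn | Placebo | CINRYZE | Difference | Power |
|---|---|---|---|---|
| none | 68.0% | 34.0% | 34.0 points | 93.4% |
| 1%, both arms | 68.3% | 34.7% | 33.7 points | 92.9% |
| 2%, both arms | 68.6% | 35.3% | 33.3 points | 92.3% |
| 5%, both arms | 69.6% | 37.3% | 32.3 points | 90.5% |
| 2%, CINRYZE only | 68.0% | 35.3% | 32.7 points | 91.2% |
| 5%, CINRYZE only | 68.0% | 37.3% | 30.7 points | 87.1% |

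The shares are assumptions; neither document gives an expected number of code breaks or pregnancies. Equal shares shrink the difference, because CINRYZE is assumed to have more working grafts to misclassify.

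**The case against.** **Other provisions soften the effect.** Graft status is sought after discontinuation (Protocol 4.5), and only unassessed subjects fail under Protocol 9.8.2.1. SAP sensitivity analyses 1 and 3 impute instead of assigning failure, and the time-to-event analysis in SAP 10.3 censors these subjects. All of this stands. But the main Fisher analysis follows the SAP 10.2 rule, which makes no use of the status collected.

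**The source is the SAP rule, which covers every dropout.** This also stands. Code breaks and pregnancies are a subset, so rewording the protocol alone would leave other working grafts scored as failures.

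**The key secondary analysis will not be run.** Correct: SAP 17 drops it after termination for futility.

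A reader might also infer more than the documents support:

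- *That withdrawal years after dosing creates TG failures.* SAP 10.1 affects only subjects without a 6-month assessment. Someone who leaves after an evaluable Month 6 biopsy keeps that result, and Protocol 7.2.2.2 asks for a biopsy from those who leave earlier.
- *That the interim cohorts would be withdrawn*, because 6.2.4 lists interim analyses among the permitted unblindings. The sentence sits among rules for individual code breaks. Section 6.2.4 limits unblinding to the DMC at the first interim and at the 50% and 75% looks, and Protocol 9.5.1 has the study continue after a positive second interim.
- *That three withdrawals would move the CINRYZE rate from 34% to 40%* (17/50 to 20/50). This needs all three to be on CINRYZE and all three to have kept their grafts. On the plan's rates, three CINRYZE withdrawals give (17 + 3 × 0.66)/50 = 18.98/50, about 38%. The number three has no source in the documents.
- *That the rule favours CINRYZE.* Equal withdrawal dilutes the difference, and the documents give no basis for expecting an imbalance in either direction.

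**Conclusion.** The inconsistency is real. Followed as written, the plan can record a failure for a subject whose graft is known to be working, and the protocol and SAP disagree on that subject's endpoint value. A subject withdrawn before Month 6 without a TG assessment is likewise scored as a TG failure.

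The likely size is small. At an assumed 1-2% withdrawn in both arms, power falls by about 0.5 to 1 point from 93.4%. At 5% it falls to 90.5% if both arms are affected, and to 87.1% if only CINRYZE is. These figures rest on the planned rates, on withdrawal unrelated to graft outcome, and on ignoring the interim looks.

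The 4-year part concerns the planned design only. The Month 6 part could still touch the TG tables that SAP 20 retains for the abbreviated report, if any subject left before Month 6 under these rules without an assessment.

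**What to change.** 1. **Protocol 6.2.4:** state that an individual emergency code break does not end scheduled outcome follow-up, and for clarity limit the withdrawal sentence to such code breaks.
2. **SAP 10.2:** use the known or adjudicated graft status of discontinued subjects, and assign failure only when status at 4 years is unknown, in line with Protocol 4.5 and 9.8.2.1. This is the change that removes the misclassification, and it covers all dropouts.
3. **Protocol 8.1.7:** reconcile with 3.2 and 4.5 so that graft and survival status is still collected. Clinical procedures for pregnant subjects are outside this comment.

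The cost is a wording change in both documents. A few unblinded subjects would remain in follow-up, but the adjudication committees stay blinded. For the abbreviated report, it is enough to identify any subject withdrawn under either rule before Month 6 and show how that subject was scored.
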